3.3.2 Rationale for GDC-6599 Dose and Schedule

The selected dose of GDC-6599 is [REDACTED]. Based on PK/PD results from the [REDACTED] of the Phase Ia/b Study GA43010, this dose is expected to [REDACTED]

[REDACTED]

[REDACTED]

At the [REDACTED] dose of GDC-6599, [REDACTED]
[REDACTED]

[REDACTED]

[REDACTED]

[REDACTED]

3.3.3 Rationale for Control Group

The placebo-controlled crossover design of this study removes patient variation by allowing the patient to serve as their own control. As a result of the inherent variability in cough and other symptoms, the use of a placebo period is necessary to assess safety and efficacy signals that may be attributable to GDC-6599. Patients will not be at increased risk during the placebo period as they will be on standard background therapy for their primary disease and will have access to rescue medication. The addition of a washout period between the two treatment periods is incorporated to prevent the carryover effect of the study drug.

3.3.4 Rationale for Biomarker Assessments

To demonstrate evidence of the biological activity of GDC-6599, biomarker assessments, before (i.e., randomization, pretreatment, baseline) and at various timepoints after treatment, will be used to identify biomarkers that may be predictive of response to GDC-6599 and/or demonstrate PD activity of GDC-6599, define PK/PD relationships, support selection of a recommended dosing regimen, and/or advance the understanding of the mechanism of action of GDC-6599 in patients on the basis of the following endpoints:

- Change from the baseline visit in biomarker levels in [REDACTED]
[REDACTED].
- Relationship among biomarker levels in [REDACTED]
[REDACTED].
- Relationship between biomarkers in [REDACTED]
[REDACTED]

During this study, [REDACTED]

[REDACTED] [*collected under prior versions of this protocol*] will be collected. [REDACTED]
[REDACTED]

Additionally, blood samples will be collected for DNA extraction (optional) to enable identification of mutations in genes encoding that are associated with chronic cough and activity of TRPA1 in the airway or can increase the knowledge and understanding of disease biology.

Exploratory research on safety biomarkers may be conducted to support future drug development. Research may include further characterization of a safety biomarker or identification of safety biomarkers that are associated with susceptibility to developing adverse events or can lead to improved adverse event monitoring or investigation.

Adverse event reports will not be derived from safety biomarker data by the Sponsor, and safety biomarker data will not be included in the formal safety analyses for this study. In addition, safety biomarker data will not inform decisions on patient management.

3.3.5 Rationale for Mannitol Challenge Test

Inhaled cough challenge models with agents that safely activate sensory neuron receptors such as TRPV1 and P2X3 are commonly performed to assess neuronal hypersensitivity, a hallmark of chronic cough and cough hypersensitivity syndrome, and to evaluate the mechanism of action of investigational therapeutics for these diseases (Morice et al. 2007; Song and Morice 2017). Activation of c-fibers with inhaled capsaicin evokes cough via TRPV1 in humans without significant bronchoconstriction, and therefore has been the most common cough challenge agent (Koskela et al. 2021; Mai et al. 2021). Activating TRPA1 ion channels in humans is more limited. TRPA1 can be stimulated by wide variety of natural products and environmental irritants but these are pungent to inhale, can cause occupational asthma, and/or are carcinogenic; acrolein in cigarette smoke, mustard oil (i.e., isothiocyanate), garlic, formalin, wasabi, and cinnamaldehyde (Belvisi et al. 2011). Due to the hydrophobic properties of TRPA1 agonists, they require dissolution in high amounts of ethanol and these amounts would be intolerable to patients with chronic cough. Cinnamaldehyde has been administered to healthy volunteers and guinea pigs, but has never been attempted in patients with asthma or chronic cough (Birrell et al. 2009). An alternative approach to stimulate TRPA1 would be to induce a change in osmolarity (e.g., with mannitol) and/or pH (e.g., with citric acid), though specificity of these challenges agents for TRPA1 is less understood. Changes in pH are known to activate TRPV1 and other acid sensing ion channels in addition to TRPA1 (Gu and Lee 2011; Mukhopadhyay et al. 2014; Joseph et al. 2021).

AHR is a key pathophysiological feature in asthma and eosinophilic COPD and is related to an increased airway smooth muscle contractility due to mast cell infiltration and eosinophilic airway inflammation. The mannitol challenge test is a clinical, indirect, osmotic bronchial challenge test using inhaled dry powder mannitol to assess the severity of AHR, a measure of asthma control, and is often used to aid the diagnosis of asthma (Sverrild et al. 2009) that correlates with the level of eosinophilic and mast cell airway inflammation that is highly predictive of the response to anti-inflammatory therapies such as inhaled corticosteroid (ICS) treatment (Lipworth et al. 2012; Anderson et al. 2016) or biologic therapies recently developed for the treatment of moderate severe asthma (Sverrild et al. 2021).

Inhaled mannitol has been shown to induce dose-dependent AHR in patients with asthma and COPD, but not in healthy volunteers (Koskela et al. 2004; Leuppi et al. 2005; Backer et al. 2020). Several studies have also demonstrated that inhalation of mannitol elicits cough in a dose-response manner and differentiates patients with CRC/UCC hypersensitivity syndrome in a disease population (Koskela et al. 2018; Nurmi et al. 2019).

The mechanism of mannitol-induced bronchoconstriction is not clearly understood. It is unknown whether mannitol-induced bronchoconstriction is due to direct activation of TRPA1 by mannitol as an irritant to sensory neurons or indirect activation due to the hyper-osmolar effect of mannitol causing mast cell degranulation and releasing inflammatory mediators (histamine, tryptase, prostaglandins) and immunomodulators, such as PGD2, capable of smooth muscle contraction and activation of TRPA1. In addition, coughing when inhaling mannitol is thought to occur due to i) dry powder inhalation stimulating mechanosensors; ii) changes in osmolarity; iii) bronchoconstriction; and iv) the release of histamine, prostaglandins from mast cells in the airways which can all directly sensitize and/or activate airway nerves and TRPA1 (Koskela et al. 2004; Anderson et al. 2016; Koskela et al. 2020). Thus, mannitol challenge could be a relevant disease model to explore the mechanism of action and efficacy of novel anti-tussive compounds.

This is relevant for TRPA1 antagonist because the TRPA1 receptor is sensitive to changes in osmolarity (Zhang et al. 2008) and blocking TRPA1 has shown to be reduce inflammation and bronchoconstriction in nonclinical models (Balestrini et al. 2021).

This study will test whether mannitol-induced AHR and cough are TRPA1 dependent and will explore mannitol-induced AHR and cough in different respiratory disease subsets. If mannitol is a TRPA1-responsive challenge agent, it may have utility in future clinical studies as a PD biomarker of TRPA1 activity. Furthermore, this study will instigate the relationship of baseline cough hypersensitivity, measured by mannitol-induced cough, with efficacy endpoints (e.g., 24-hour cough count) and inform the use of mannitol-induced AHR or cough as prognostic biomarkers for a personalized approach to treatment with a TRPA1-specific therapy such as GDC-6599.

3.3.6 Rationale for 24-Hour Cough Monitoring and Continuous Digital Cough Assessment

Cough will be assessed by the VitaloJAK semi-automated cough counting system. VitaloJAK is the only clinically validated, 510K-cleared, and Conformité Européenne-marked medical device system for the objective measurement of cough (Birring et al. 2008; Barton et al. 2012; Smith et al. 2021). VitaloJAK has been used to measure cough frequency as either a primary or secondary endpoint in several Phase II and III programs, including gefapixent, BAY1817080, and BLU-5937, targeting patients with UCC or CRC. The treatment effect in this study will be analyzed on the basis of cough frequency data (24-hour OCC) collected via VitaloJAK.

While VitaloJAK is the current gold standard for measuring cough frequency, it is limited to a maximum of 24-hour recordings. Previous placebo-controlled studies suggest there is significant day-to-day variability in 24-hour OCC that reduces the probability of detecting treatment differences based upon a single 24-hour data collection. [REDACTED]

[REDACTED]

[REDACTED]

4. MATERIALS AND METHODS

4.1 PATIENTS

Approximately 80 patients with five distinct subsets of chronic cough will be enrolled in this study (Part A and Part B). Potential patients are eligible to be included in the study only if all of the general inclusion criteria (Section 4.1.1.1) and the criteria for their respective disease background (Section 4.1.1.2 or Section 4.1.1.4) are met.

Table 2 Planned Study Enrollment

Study	Cohort	Approximate No. of Patients per Cohort
Part A	CRC with asthma \pm atopy	30
	UCC	30
Part B	CRC COPD \pm CB	20
Total enrollment		80

COPD=chronic obstructive pulmonary disease; COPD \pm CB=chronic obstructive pulmonary disease with *or without* chronic bronchitis; CRC=chronic refractory cough; UCC=unexplained chronic cough.

4.1.1 Inclusion Criteria

4.1.1.1 General Inclusion Criteria for All Patients

Patients must meet the following criteria for study entry:

- Signed Informed Consent Form
- Age 18–80 years at time of signing Informed Consent Form (except patients with COPD \geq 40 years old)

- Ability to comply with the study protocol
- Body mass index (BMI) of 17–35 kg/m² at screening
- *A Persistent cough that has lasted for at least 1 year, and refractory despite optimized treatment for asthma, COPD, GERD, or UCC for at least 12 weeks* (see CHEST 2018/ERS 2020 guidelines [Irwin et al. 2018; Morice et al. 2020].
- Chest X-ray or computed tomography (CT) scan thorax within 5 years prior to screening visits that confirms, *in the opinion of the investigator*, the absence of any clinically significant abnormality contributing to the chronic cough, *with the exception of COPD for patients with CRC COPD with or without CB* (see Section 4.1.1.4)
- Cough severity VAS score ≥40 at screening
- Pre-bronchodilator forced expiratory volume in 1 second (FEV₁) ≥60% of predicted value at screening
- Mannitol CDR ≥12 coughs per 100 mg of mannitol determined at screening mannitol challenge test, based on manual cough counting
- Demonstrated ability to use and comply with electronic patient-reported outcome (ePRO) requirements, defined as completion of all questions on at least 2 out of 7 consecutive days within the 14 days during screening

Patients unable to demonstrate compliance with completing the electronic daily assessments (Numeric Response Scale [NRS] and VAS on ePRO) within the first 2 weeks of screening will be screen failed. Patients will have the opportunity to demonstrate ePRO compliance if re-screened.

- For women of childbearing potential: agreement to remain abstinent (refrain from heterosexual intercourse) or use contraception, as defined below:

Women must remain abstinent or use contraceptive methods with a failure rate of <1% per year during the treatment period and for [REDACTED] after the final dose of study drug, or for the period required by local guidelines or regulations, whichever is longer.

A woman is considered to be of childbearing potential if she is postmenarchal, has not reached a postmenopausal state (≥12 continuous months of amenorrhea with no identified cause other than menopause), and is not permanently infertile due to surgery (i.e., removal of ovaries, fallopian tubes, and/or uterus) or another cause as determined by the investigator (e.g., Müllerian agenesis). Per this definition, a woman with a tubal ligation is considered to be of childbearing potential. The definition of childbearing potential may be adapted for alignment with local guidelines or regulations.

Examples of contraceptive methods with a failure rate of <1% per year include bilateral tubal ligation, male sterilization, hormonal contraceptives that inhibit ovulation, hormone-releasing intrauterine devices, and copper intrauterine devices.

The reliability of sexual abstinence should be evaluated in relation to the duration of the clinical trial and the preferred and usual lifestyle of the patient. Periodic abstinence (e.g., calendar, ovulation, symptothermal, or postovulation methods) and withdrawal are not adequate methods of contraception. If required per local guidelines or regulations, locally recognized adequate methods of contraception and information about the reliability of abstinence will be described in the local Informed Consent Form.

4.1.1.2 Inclusion Criteria for Patients with CRC with Atopic Asthma or Patients with CRC with Non-Atopic Asthma (Part A)

Patients with CRC with atopic asthma or patients with CRC with non-atopic asthma must meet the following criteria for study entry:

- Physician diagnosis of asthma for ≥ 12 weeks based upon GINA STEP 2–5
- Stable treatment with ICS therapy (GINA STEP 2) or ICS therapy and at least one additional controller (GINA STEP 3–5) for ≥ 12 weeks
- Patients with atopic asthma, based upon historic record of positive test for atopy (if available), or confirmed at screening by *any positive test result from a panel of standard allergens including cat dander, dog dander, cockroach, dust mite, mold, and relevant local allergens, as determined through use of ImmunoCAP™ Specific IgE test, skin prick test, or radioallergosorbent test (RAST)*
- Patients with non-atopic asthma, based upon historic record of negative test for atopy (if available), or confirmed at screening by *negative test result across chosen atopy testing panel and no history or symptoms suggesting atopy*
- *No history of smoking or former smoker with smoking history of <20 pack-years or equivalent history*

Smoking is defined as use of inhaled tobacco or cannabis products (e.g., cigarettes, cigars, electronic cigarettes, vaporizing devices, or pipes).

A former smoker is defined as someone with smoking history who has not used inhaled tobacco or cannabis products within 6 months prior to screening.

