24-hour OCC=objective cough count over 24 hours; AHR=airway hyperresponsiveness, expressed as RDR (calculated as maximum percent decrease in FEV₁ [relative to baseline of mannitol challenge] after the last dose of mannitol divided by cumulative dose of mannitol, and PD15 (defined as provoking dose of mannitol that induces a 15% decrease in FEV₁); CDR=coughs-per-dose ratio, calculated as total number of provoked coughs divided by cumulative dose of mannitol and expressed as coughs per 100 mg of mannitol; CRC=chronic refractory cough; DAIDS=Division of AIDS; FEV₁=forced expiratory volume in 1 second; NRS=Numeric Response Scale; PK=pharmacokinetic; RDR=response-dose ratio; UCC=unexplained chronic cough; TRP=transient receptor potential; TRPA1=TRP ankyrin 1; VAS=visual analog scale.

^a Adverse events will be graded according to the DAIDS Table for Grading the Severity of Adult and Pediatric Adverse Events (HSS 2017), with slight modifications for clarity and for alignment with internal practices (see Section 5.3.3 and [Appendix 10](#)).

Table 1 Objectives and Corresponding Endpoints (cont.)

Exploratory Objectives (cont.)	Corresponding Endpoints (cont.)

 To evaluate mannitol-induced airway smooth muscle hyper-responsiveness as a measure of TRPA1 airway activity and treatment benefit of GDC-6599, compared with placebo, in patients with CRC with asthma or UCC 	
 Change in mannitol-induced AHR from baseline to Day 14

 To evaluate the efficacy of GDC-6599, as compared with placebo, across each chronic cough disease subgroup 	
 Change in 24-hour OCC collected using the VitaloJAK cough recorder from baseline to Day 14 [REDACTED] Change in FEV_1 from baseline to Day 14 [REDACTED] Change in the severity of cough, as assessed through the use of the patient-reported cough severity VAS score, from baseline to Day 14 Change in the severity of cough, as assessed through the use of the patient-reported cough severity NRS score, from baseline to Day 14 [REDACTED]

 To evaluate cough hypersensitivity and AHR to mannitol across chronic cough disease subgroups 	
 CDR to mannitol across patients with different background diseases AHR to mannitol across patients with different background diseases

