3.3 RATIONALE FOR STUDY DESIGN

3.3.1 Rationale for Patient Population

Three cohorts of chronic cough patients with different disease backgrounds (CRC asthma *with or without atopy*, UCC, or CRC COPD) will be enrolled in this study to assess the potential heterogeneity of *treatment effects on cough frequency across disease backgrounds*. *The study will also explore potential heterogeneity of baseline cough hypersensitivity to inhaled mannitol and the relationship with baseline cough frequency.*

Cough is an important symptom of chronic lung disorders and is often cited by patients with CRC with asthma, CRC with COPD, or idiopathic pulmonary fibrosis as the most bothersome of respiratory symptoms having an adverse impact on HRQoL (Polley et al. 2008) and is a key aspect of disease burden and control (Marsden et al. 2016). Despite the high unmet need, there are currently no approved drugs for the treatment of CRC with asthma, UCC, or CRC with COPD.

Chronic cough, despite adherence to guideline-based standard-of-care treatment, represents high unmet medical need in patients with CRC with asthma, UCC, or CRC with COPD. Cough hypersensitivity to inhaled irritants is a key feature of chronic cough. This study will target patients with CRC with atopic asthma, CRC with non-atopic asthma, UCC, and CRC COPD. Patients must have a diagnosis of chronic cough based upon consensus guidelines (American College of Chest Physicians [CHEST] 2018;

European Respiratory Society [ERS] 2020). A mannitol CDR of at least 12 coughs/100 mg is required for inclusion in this study (see Section 4.1.1) in order to identify patients with cough hypersensitivity and avoid including patients with very low mannitol-evoked cough responses, in whom a treatment effect would be difficult to demonstrate.

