4.5.5 Mannitol Challenge Test

The mannitol challenge test is a commercially approved bronchial challenge test kit containing pre-filled mannitol capsules and a handheld dry powder inhaler device. During a mannitol challenge test, patients will orally inhale increasing doses of mannitol. After each dose, airway parameters will be measured by spirometry. Inhalation of mannitol doses will continue until all doses (cumulative 635 mg) are inhaled, *there is a ≥15% decrease in FEV₁ relative to baseline, or there is a ≥10% decrease in FEV₁ between two successive doses. The mannitol challenge test is required at Study Visit 1 (screening) and optional at Study Visits 4 and 7 (see Section 4.5.14).* Details regarding conduct of mannitol challenge are provided in the mannitol challenge test guidance.

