6.4 EFFICACY ANALYSES

The purpose of this study is estimation and hypothesis generation regarding efficacy and activity of GDC-6599, as compared with placebo, in patients with CRC with asthma or UCC. The effects of GDC-6599 on cough will also be assessed in a subgroup of patients with CRC with COPD. Statistical summaries will be descriptive in nature (e.g., incidence rates, means, standard deviations, and percentiles). Any patients who received any amount of GDC-6599 or placebo will be included in the analyses. Patients will be grouped according to the treatment received in a given period. Final results will be summarized for GDC-6599 and for the placebo periods. No formal hypothesis testing will be performed.

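### Mannitol CDR is compared across diseases only in patients selected on CDR ≥12, so the exploratory comparison is distorted as a description of the diseases; with similar spreads it understates differences

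*Combined protocol and SAP*

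**What the plan says.** Section 4.1.1.1 sets one threshold for all three cohorts: "Mannitol CDR ≥12 coughs per 100 mg of mannitol determined at screening mannitol challenge test". Section 3.3.1 explains that the threshold identifies patients with cough hypersensitivity and serves to "avoid including patients with very low mannitol-evoked cough responses, in whom a treatment effect would be difficult to demonstrate".

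The protocol also wants to profile CDR by disease. Table 1 in Section 2 lists "CDR to mannitol across patients with different background diseases", with a matching endpoint for airway hyperresponsiveness (AHR). Section 3.3.1 adds that the study will "explore potential heterogeneity of baseline cough hypersensitivity to inhaled mannitol and the relationship with baseline cough frequency".

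On timing, Section 4.5.5 states: "The mannitol challenge test is required at Study Visit 1 (screening) and optional at Study Visits 4 and 7". CDR is therefore measured before the threshold is applied.

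On the analysis set, Section 6.4 states: "Any patients who received any amount of GDC-6599 or placebo will be included in the analyses". It also says that summaries are descriptive and that no hypothesis is tested. Sections 6.5 and 6.6 define safety and PK sets. Nothing in Section 6 defines a set for the cross-disease mannitol endpoints.

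**The concern.** The threshold suits a treatment-effect study, because patients who barely cough to mannitol tell little about an antitussive. The cross-disease objective asks something else: how sensitive patients with asthma, UCC or COPD are. Answering it in enrolled patients compares distributions cut off at 12, and the disease with the lower CDR loses more of its lower tail. The share of patients passing the threshold is itself a disease difference, and an enrolled-only analysis discards it.

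At stake is the profiling aim. Section 3.3.5 links it to possible use of mannitol response as a prognostic biomarker. A real disease difference could look small, or an apparent one could come from selection. AHR is affected to the extent that it correlates with CDR.

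**Working it through.** **Inputs.** From the protocol: threshold 12 coughs per 100 mg, all cohorts (Section 4.1.1.1); planned cohorts of about 30, 30 and 20 (Table 2). The protocol gives no mean, SD or pass rate for CDR by disease and no figure to reproduce. Assumed: log-normal CDR, geometric means (GM) 6 to 48, log-SD 0.6 to 1.2.

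**Formula.** For log CDR with mean μ and SD s, cut at c = ln 12 = 2.485, let k = (c − μ)/s and λ = φ(k)/(1 − Φ(k)). The mean log CDR among patients at or above the cut is μ + sλ.

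**Worked case: GM 12 v 24, log-SD 0.8.**
- Lower disease: μ = 2.485, k = 0, λ = 0.798, truncated mean 2.485 + 0.8 × 0.798 = 3.123, GM 22.7; 50% pass.
- Higher disease: μ = 3.178, k = −0.866, λ = 0.340, truncated mean 3.178 + 0.8 × 0.340 = 3.450, GM 31.5; 81% pass.
- Ratio seen: 31.5/22.7 = 1.39 against a true 2.00. The share of the log difference retained is ln 1.39/ln 2.00, about 47%.

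**Equal log-SD, true ratio 2.0: ratio seen in enrolled patients**

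| GMs | SD 0.6 | SD 0.8 | SD 1.0 | SD 1.2 |
|---|---|---|---|---|
| 6 v 12 | 1.20 | 1.22 | 1.23 | 1.24 |
| 8 v 16 | 1.27 | 1.28 | 1.28 | 1.28 |
| 12 v 24 | 1.43 | 1.39 | 1.36 | 1.35 |
| 16 v 32 | 1.56 | 1.48 | 1.44 | 1.41 |
| 24 v 48 | 1.77 | 1.64 | 1.56 | 1.51 |

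A true ratio of 1.5 (12 v 18 or 16 v 24) appears as 1.18 to 1.26. Across all these cases, 26% to 82% of the log difference is retained.

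**Unequal log-SD: the direction is not fixed**

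| Disease A: GM (SD) | Disease B: GM (SD) | True ratio B/A | Seen |
|---|---|---|---|
| 16 (0.6) | 16 (1.0) | 1.00 | 1.37, created |
| 12 (0.6) | 18 (1.0) | 1.50 | 1.63, inflated |
| 12 (1.0) | 18 (0.6) | 1.50 | 0.87, reversed |

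**CDR and baseline cough frequency.** Assume a bivariate normal relationship on suitable scales with true correlation r = 0.5. Cutting the lower tail of CDR leaves a fraction v = 1 + kλ − λ² of its variance, and the correlation becomes r√v/√(r²v + 1 − r²).

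| Lowest share cut | v | Correlation seen |
|---|---|---|
| 20% | 0.583 | 0.40 |
| 40% | 0.422 | 0.35 |
| 60% | 0.312 | 0.31 |

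The mean of cough frequency at a given CDR does not change when low CDR values are removed. The slope of cough frequency on CDR therefore stays at 0.50 in all three rows.

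**A truncated-distribution model on enrolled data.** Simulated maximum-likelihood fits with common SD, GM 12 v 24, log-SD 0.8 and 30 patients per disease gave ratio estimates whose central 95% ran from about 1.1 to about 5. With 30 v 20 the upper end was between 5 and 6. The upper end varied between runs, but the model is too imprecise at this size to be the main answer.

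**The case against.** The strongest reply has four parts.

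1. **The objective is modest.** It is exploratory and descriptive, with no ratio or test specified. Section 3.3.1 openly restricts the study to patients with cough hypersensitivity, and describing CDR among such patients is a legitimate conditional question. This stands, and it limits the severity. But the protocol does not label the comparison as conditional, and Section 3.3.1 speaks of heterogeneity of baseline sensitivity across diseases. The dosed-patient sentence sits under efficacy analyses, so applying it to baseline profiling is an inference. It is nevertheless the only set on offer, and any enrolled-patient set has passed the same threshold.

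2. **The direction is unknown.** A reader might infer that the comparison always understates disease differences. The documents do not support that: it needs similar log-scale spreads, and they give no spreads.

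3. **The wider data may not exist.** A reader might infer that untruncated data are already in hand. Section 4.5.5 shows that CDR is measured at screening. Section 4.5.1 promises only a record of eligibility or reasons for failure, not the CDR values of screen failures. Nor does a 24-hour recording necessarily exist for them: under Appendix 1, footnotes a and w, single-day screening starts the recorder at least 30 minutes after the challenge, when a failing CDR may already be known. The tested set is also not free of selection, since Section 5.1.2.1 advises against the challenge at very low lung function and patients depend on referral.

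4. **The relationship with cough frequency need not be biased.** Section 3.3.1 specifies no correlation, and a slope on CDR survives the threshold. This stands.

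**Conclusion.** The concern holds for the exploratory cross-disease comparison. Every enrolled patient is selected on the variable being compared, for a reason that concerns treatment effects, and the plan neither says so nor handles it.

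The size rests on assumed distributions. With log-normal CDR, equal log-SD of 0.6 to 1.2 and lower-disease geometric means of 8 to 24, a true ratio of 2.0 appears as about 1.3 to 1.8; at a geometric mean of 6 it falls to about 1.2. With unequal spreads the error can go either way, and enrolled data alone would not reliably show which. The effect on AHR depends on its correlation with CDR and has not been quantified. For cough frequency, only a correlation is attenuated.

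A reader might also infer that the primary result is compromised. It is not: the drug-placebo contrast is within patient, and the threshold does not bias it for the population enrolled. This is a worthwhile, low-cost improvement to exploratory objectives.

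**What to change.** For the cross-disease mannitol objectives only:

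- Enter screening CDR, response-dose ratio and disease group in the study database for every consented patient who completes the screening challenge, including screen failures. Use one test per patient, chosen by a stated rule, where someone is re-screened.
- Compare CDR and AHR across diseases in that set, and report the proportion with CDR ≥12 per disease.
- Label any enrolled-only comparison as conditional on CDR ≥12.
- Relate baseline cough frequency to CDR by regression on CDR. Use screening 24-hour counts from screen failures only where a recording was already made.
- Do not rely on a truncated-distribution model as the main fallback at 20 to 30 patients per cohort.

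The cost is a few eCRF fields for screen failures, consent wording that covers this use, and a short analysis-set definition. The set remains selected on who is referred and on the lung function needed for the challenge, which the report should say. No procedure is added. The change is best made before further screening, because values not captured then may not be recoverable.
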